If the SAE is not previously documented in the SmPC a local DS&E Department associate may urgently require further information from the treating physician or other involved health care professional for health authority reporting.

Pregnancy

This study is in postmenopausal women, so pregnancy should not occur. However, as is routine, to ensure patient safety, any occurrence of a pregnancy in a patient on Afinitor (everolimus; RAD001) must be reported to Novartis within 24 hours of learning of its occurrence. Any SAE experienced during pregnancy must be reported on the SAE Report Form. The pregnancy should be followed up to determine outcome, including spontaneous or voluntary termination, details of the birth, and the presence or absence of any birth defects, congenital abnormalities, or maternal and/or newborn complications.

Pregnancy should be recorded on a Pregnancy Form and reported by the treating physician or other involved health care professional to the local Novartis DS&E Department. In case of any congenital abnormality, birth defect or maternal and newborn complications, the possible relationship to the Novartis drug of interest should be reported.

12 Plans for disseminating and communicating study results

Upon study completion and finalisation of the study report, the results of this NIS may be submitted for publication and/or posted in a publicly accessible database of results. Publications will comply with internal Novartis standards and the International Committee of

Medical Journal Editors guidelines. For non-interventional PASS studies, the final manuscript will be submitted to EMA and the competent authorities of the Member States in which the product is authorised within two weeks after first acceptance for publication.

13 References

Abraham RT, Gibbons JJ (2007) The Mammalian Target of Rapamycin Signaling Pathway: Twists and Turns in the Road to Cancer Therapy. Clin Cancer Res; 13: 3109-3114.

Aromasin Prescribing Information; Pfizer-Pharnacia 2005/USPI; American SmPC August 2008 (UK as RMS for EU MRP).

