7.2.1 Stomatitis

Stomatitis is a very common adverse event of therapy with Afinitor and exemestane, often occurring soon after starting treatment and frequently regressing during the course of treatment [Porta 2011]. The frequency of all grade stomatitis and related events from the BOLERO-2 study was higher in the Afinitor and exemestane arm (67%) than in the control arm (12%). Grade 3 events occurred in 8% and <1% of patients, respectively but no grade 4 events were observed.

In the Afinitor and exemestane arm, more than one-third of all stomatitis events (grade \geq 2) were reported in the first two weeks (cumulative risk, 14%). The cumulative risks of stomatitis at six and 48 weeks were 26% and 37%, respectively, for Afinitor and exemestane versus 3% for exemestane and placebo (Figure 1 below).

Figure 1: Cumulative risk estimates for initial onset of grade 22 stomatitis [Rugo 2014]

Abbreviations: EVE, everolimus; EXE, exemestane; PBO, placebo.

Among 39 patients with grade \geq 3 stomatitis in the Afinitor plus exemestane arm, 97% experienced resolution to grade \leq 1 following dose interruption/reduction after a median of 3.1 weeks, and 82% had complete resolution after a median of 7.4 weeks. In the control arm, the median time to resolution from grade 3 to grade \leq 1 was 2.6 weeks (time to complete resolution was not assessable; one of two patients had complete resolution).

In the acute phase, various options are available to the physician to provide relief for the patient. The nature and duration of treatment depend on the degree of severity of the stomatitis and the specific criteria used by the individual physician. Since the data are as yet unclear, no definitive treatment recommendation for stomatitis with Afinitor can be provided. However, stomatitis occurring under treatment with mTOR inhibitors has been seen to differ in nature from the stomatitis that develops under certain chemotherapies. For this reason,

this NIS will record the measures used for prophylaxis and, if necessary, treatment of stomatitis and the outcome of these measures. The study will also attempt to identify predisposing risk factors.

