9.3 Variables

9.3.1 Patient demographics and other baseline characteristics

In this non-interventional study, diagnostic measures and medically indicated examinations are documented only if they were conducted in accordance with normal routine practice. Prior to enrolment into this study, it is necessary to obtain the patient's written informed consent. Patients can be consented up to four weeks after treatment with Afinitor plus exemestane is initiated. The study aims to collect the following parameters at baseline where available:

- European Cooperative Oncology Group (ECOG) Performance Index if conducted
- General demography including age and gender;

- Medical history and current medical conditions;
- Concomitant medications;
- History and current disease status (including ER, PgR and Ki67 status if available, date of original diagnosis, date of first metastatic relapse if applicable and site involvement);
- Previous anticancer treatments for metastatic disease. The following information must be collected if available for all previous anticancer therapies: start date, end date, best response and reason for treatment discontinuation. Any history of stomatitis whilst on cancer therapy will also be collected if possible.
- Date of the prescription of Afinitor plus exemestane including dosage, reason for prescribing, date on which treatment will commence;
- Details of any planned prophylactic measures for stomatitis;
- EQ-5D questionnaire and subjective well-being assessment.

To determine eligibility at the screening visit, the following assessments may be performed and information captured:

- Physical examination and weight;
- Vital signs including blood pressure and heart rate;
- Safety laboratory assessments such as haematology, biochemistry, serum lipid profile, coagulation and urinalysis should be performed locally at the Investigator's discretion. Hepatitis screening will include: hepatitis B virus DNA, hepatitis B surface antigen, hepatitis B surface antibody, hepatitis B core antibody and hepatitis C virus ribonucleic acid polymerase chain reaction. If, at screening, laboratory results are out of range and clinically significant, these results should be captured on the medical history/current medical conditions eCRF;
- Tumour assessments at baseline may include clinical examination or radiographic or laboratory features, mirroring routine practice.

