9.3.4.6 Adverse events

Safety will be monitored by assessing all AEs, including Serious Adverse Events (SAEs), the regular monitoring of haematology, blood chemistry, vital signs and physical condition. These assessments should be performed continuously throughout the study.

An AE is any undesirable sign, symptom or medical condition occurring after starting study drug (or therapy) including death. Medical conditions or diseases present before starting the study are only considered AEs if they worsen after starting the study.

A SAE is an undesirable sign, symptom or medical condition which: 1. is fatal or lifethreatening; 2. requires or prolongs hospitalisation; 3. results in persistent or significant disability/incapacity; 4. constitutes a congenital anomaly or a birth defect; 5. is medically significant, in that it may jeopardise the patient and may require medical or surgical intervention to prevent one of the outcomes listed above.

Toxicity will be assessed using the NCI-CTCAE, version 4.03 (CTCAEv4.03, http://evs.nci.nih.gov/ftp1/CTCAE/CTCAE_4.03_2010-06-14_QuickReference_8.5x11.pdf).

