9.7 Data analysis

All analyses will be performed by Novartis or a contracted designee.

All the patients enrolled in the study will be analysed. The reference population for analysis will be patients who were enrolled and received follow-up, meeting eligibility criteria with at least one follow-up visit completed.

Each Investigator taking part in the study should enroll at least one patient and not more than 15 patients will be enrolled per centre. The enrolment period is one year, however this can be re-assessed depending on how recruitment is progressing. Data from all centres that participate in this protocol will be combined for analysis.

Descriptive statistics will be provided unless otherwise specified. These include n, mean, standard deviation, median and ranges for continuous, quantitative variables and frequencies and percentages for categorical, qualitative variables. For patients with screening assessments who do not enter the treatment period, data will only be listed. Further technical details and discussion of the following statistical considerations will appear in the statistical analysis plan, which will be finalised prior to database lock and the analysis.

For all analyses, baseline value will be defined as the latest assessment prior to first study drug administration.

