Essential written and electronic documents should be retained for at least15 years from the completion of the Clinical Trial unless Novartis provides written permission to dispose of them, or requires their retention for an additional period of time because of applicable laws, regulations and/or guidelines.

Confidentiality

The Investigator must ensure anonymity of the patients; patients must not be identified by names in any documents submitted to Novartis. Signed informed consent forms and patient enrolment log must be kept strictly confidential to enable patient identification at the site.

Audits and inspections

Source data/documents must be available for inspections by Novartis or their designee, IECs or Health Authorities.

11 Management and reporting of adverse events

All AEs including SAEs and safety endpoints, where relevant, must be collected and recorded in the study database, irrespective of causal association. Adverse Drug Reactions (ADRs) occurring in association with exposure to a Novartis drug other than the Novartis drug of interest, can be reported to the local Health Authority in accordance with national regulatory requirements for individual case safety reporting or to Novartis DS&E as a spontaneous report.

Adverse events identified for non-Novartis products should be reported to the local health authority in accordance with national regulatory requirements for individual case safety reporting or the Marketing Authorisation Holder; these will not be recorded in the Novartis safety database.

Adverse event reporting

An AE is defined as the appearance of (or worsening of any pre-existing) undesirable sign(s), symptom(s), or medical condition(s) that occur after patient's signed informed consent has been obtained. Abnormal laboratory values or test results occurring after informed consent constitute AEs only if they induce clinical signs or symptoms, are considered clinically significant, require therapy (e.g. haematologic abnormality that requires transfusion or haematological stem cell support), or require changes in study medication(s).

Confidential

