Medical conditions or diseases present before starting the study are only considered AEs if they worsen after starting the drug of interest. Adverse events that begin or worsen after the start of this study should be recorded in the AE eCRF. Conditions that were already present at the time of informed consent should be recorded in the Medical History eCRF. Adverse Event monitoring should be continued for at least 30 days following the end of the study. Adverse Events (including laboratory abnormalities that constitute AEs) should be described using a diagnosis whenever possible, rather than individual underlying signs and symptoms. When a clear diagnosis cannot be identified, each sign or symptom should be reported as a separate AE.

Adverse events will be assessed according to the CTCAE version 4.0. If CTCAE grading does not exist for an AE, the severity of mild, moderate, severe, and life-threatening, corresponding to grades 1-4, will be used. CTCAE grade 5 (death) will not be used in this study; rather, information about deaths will be collected on a death form.

An AE can, therefore, be any unfavourable and unintended sign (including an abnormal laboratory finding), symptom, or disease temporally associated with the use of Afinitor, whether or not related to the medicinal product(s).

The occurrence of AEs should be sought by non-directive questioning of the patient at each visit during the study. Adverse Events also may be detected when they are volunteered by the patient during or between visits or through physical examination, laboratory test, or other assessments. All AEs must be recorded on the AE eCRF with the following information:

- the severity grade (1-4);
- its relationship to the drug(s) of interest (suspected or not suspected);
- its duration (start and end dates or if continuing at final examination);
- whether it constitutes a SAE.

In addition, all reports of the following special scenarios are considered an AE irrespective of whether a clinical event has occurred:

- Drug-drug or drug-food interaction;
- Drug exposure during pregnancy;
- Drug use during lactation or breast-feeding;
- Lack of effectiveness;
- Overdose;
- Drug abuse and misuse;
- Drug maladministration or accidental exposure;
- Dispensing errors or medication errors;
- Off-label use;
- Withdrawal or rebound symptoms.

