For Afinitor the following AEs are of special interest for targeted follow-up and should be notified to Novartis Drug Safety and Epidemiology (DS&E) in the same manner as a SAE:

- Acute and congestive heart failure
- Developmental toxicity
- Afinitor amenorrhoea
- Afinitor reactivation, aggravation, exacerbation of background disease
- Afinitor NIP
- Afinitor severe infections including hepatitis reactivation
- Pregnancy and breast-feeding women
- Hypersensitivity including anaphylaxis
- Malignancy and neoplasm
- Renal impairment or failure.

To ensure patient safety, every SAE, regardless of causality assessment, occurring after the patient has provided informed consent and until 30 days after the patient has stopped study participation must be reported to Novartis within 24 hours of learning of its occurrence.

Any SAEs occurring after this 28 day period should only be reported to Novartis if the treating physician or other involved health care professional suspects a causal relationship to the drug of interest.

Recurrent episodes, complications, or progression of the initial SAE must be reported as a follow-up to the original episode, regardless of when the event occurs. This report must be submitted within 24 hours of the treating physician or other involved health care professional receiving the follow-up information. An SAE considered completely unrelated to a previously reported one should be reported separately as a new event.

Information about all SAEs is collected and recorded on the SAE Report Form. The treating physician or other involved health care professional must assess the relationship to the drug of interest, complete the SAE report form and send the completed signed form within 24 h to the local Novartis Drug Safety & Epidemiology (DS&E) Department.. The telephone number of the contact persons in the local department of DS&E, specific to the site, are listed in the treating physician or other involved health care health care professional folder provided to each site.

Follow-up information is collected and sent in the same manner as for the original SAE Report, using a new SAE form, stating that this is a follow-up to the previously reported SAE and giving the date of the original report. The follow-up information should describe whether the event has resolved or continues, if and how it was treated, and whether the patient continued or withdrew from study participation.

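### Adverse events start at first dose in Section 9.3.4.6 but at signed consent in Section 11, and consent may come four weeks after first dose, so early stomatitis may go uncounted

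*Protocol*

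**What the plan says.** Two rules stand side by side in the protocol.

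- **From first dose.** Section 9.3.4.6: "An AE is any undesirable sign, symptom or medical condition occurring after starting study drug (or therapy) including death". Section 9.1 likewise starts each patient's observation period at initiation of treatment.
- **From consent.** Section 11, under adverse event reporting, limits the definition to signs, symptoms or "medical condition(s) that occur after patient's signed informed consent has been obtained". It then directs: "Conditions that were already present at the time of informed consent should be recorded in the Medical History eCRF". Serious events are reportable when "occurring after the patient has provided informed consent and until 30 days after the patient has stopped study participation".

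The two start points differ whenever consent follows the first dose, which the protocol permits. Section 9.3.1: "Patients can be consented up to four weeks after treatment with Afinitor plus exemestane is initiated". The footnote to the follow-up schedule in Section 9.1 and the consent text in Section 10 repeat the four-week allowance.

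Incidence and time to onset of stomatitis and non-infectious pneumonitis (NIP) are primary outcomes (Sections 8.1, 9.3.2 and 9.7.1). In the follow-up schedule the adverse event row is blank at the start of documentation and begins at about two weeks.

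**The concern.** No sentence says which definition governs, and Section 11 is the section that tells sites which page to complete. A site that follows it for a patient consented after first dose would enter stomatitis still present at consent as medical history. Stomatitis that began and resolved before consent fits neither the Section 11 definition nor its rule for conditions already present. No instruction tells sites to go back over the interval from first dose to consent and record events on the adverse event page.

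That interval is when stomatitis is most frequent: Section 7.2.1 describes onset soon after starting treatment. Leaving it out biases incidence down and onset late, by an amount that depends on each site's consent habits. Section 8 motivates the study by UK reports of more adverse events than in the earlier phase III trial, and it wants the time course in order to inform monitoring. A downward, delayed bias works against both aims. The analysis plan cannot repair it, because events never recorded with an onset date and grade are not in the database.

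**Working it through.** **Inputs.** Cumulative risk of grade 2 or worse stomatitis in the earlier phase III trial: 14% at week 2, 26% at week 6, 37% at week 48 (Section 7.2.1). All-grade planning incidences: 56%, 59% and 71% (Section 9.5). Planned N = 200 with exact 95% limits (Table 9-4). Latest consent: week 4. The share of patients consenting late is not given; it is called *f* and varied.

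**Step 1: planned precision.** Clopper-Pearson limits are the 0.025 quantile of Beta(x, n−x+1) and the 0.975 quantile of Beta(x+1, n−x). For 80/200 they are 33.15% and 47.15%, against 33.2% and 47.2% in Table 9-4. All eight rows agree to within 0.1 point. The planned precision of about ±7 points is correct.

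**Step 2: share of 48-week first events before consent.**
- Consent at week 2: 14/37 = 38%.
- Consent at week 4: linear interpolation (assumed) gives 14 + (26 − 14) × 2/4 = 20%, so 20/37 = 54%. Because cumulative risk cannot fall, the week-4 share lies between 14/37 = 38% and 26/37 = 70%.

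**Step 3: observed grade 2 or worse incidence under the Section 11 rule.** Observed = 37 − *f* × (cumulative risk at consent). Everyone else is assumed to consent on or before first dose, and no patient with an event before consent is counted later.

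| Share consenting late | at week 2 | at week 4 |
|---|---|---|
| 25% | 33.5% | 32.0% |
| 50% | 30.0% | 27.0% |
| 100% | 23.0% | 17.0% |

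An observed 30% (60/200) has limits 23.7% to 36.9% in Table 9-4, which just exclude the true 37%. The loss equals the planned 7 points at *f* = 7/14 = 50% for week 2 and *f* = 7/20 = 35% for week 4.

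**Step 4: all grades.** Suppose the grade 2 or worse timing holds for all grades (an assumption). Then observed = p × (1 − *f* × s), where s is the share from Step 2. With p = 59% and *f* = 50%:
- week 2: 59 × (1 − 0.5 × 0.378) = 47.8%
- week 4: 59 × (1 − 0.5 × 0.541) = 43.1%

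The loss reaches 7 points at *f* = 0.07/(0.59 × 0.378) = 31% for week 2 and 0.07/(0.59 × 0.541) = 22% for week 4.

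**Step 5: NIP.** Section 7.2.2 gives a 5% cumulative risk of grade 2 or worse events at 12 weeks and describes few early events. Even accrual over those weeks (assumed) would put 5 × 4/12 = 1.7 points before week 4.

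**The case against.** Several points on the other side are sound.

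- **Section 11 is not the settled rule.** A reader might infer that the protocol counts events only from consent. It does not establish that. Section 9.3.4.6 and the observation period both start at treatment, Section 9.7.1 analyses any instance of the two toxicities, and Section 11 itself also describes an adverse event as one temporally associated with Afinitor use. What stands is an unresolved contradiction: early events could be lost, but the text does not show that they will be.
- **Some early events may be captured elsewhere.** Medical records are a data source (Section 9.4), and any history of stomatitis during cancer therapy is collected at baseline if possible (Section 9.3.1). That item does not require grade, onset date or duration, so it cannot supply the primary outcome.
- **The losses are upper bounds.** Stomatitis that worsens after consent, or a new episode, still counts under Section 11. Such patients return to the incidence numerator, but with an onset that is too late. The 17% result needs every patient to consent at the last permitted moment, and the 30% result needs half to consent at week 2. Neither is a forecast.
- **The timing data cover grade 2 or worse only.** Applying them to all-grade incidence is an assumption.

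None of this removes the conflict or tells a site which page to use.

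**Conclusion.** The defect stands as a contradiction in the adverse event start point that bears on a primary outcome. If Section 11 is followed for late-consented patients, between 38% (week 2) and about 54% (week 4; bounds 38% to 70%) of 48-week first grade 2 or worse stomatitis events begin before the adverse event window opens. Incidence is then biased down and onset late. The size depends on the unknown share and timing of late consent, on the earlier trial's time course applying here, and on how many affected patients worsen or relapse after consent. At worst the loss exceeds the planned 7-point precision.

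Three wider inferences are not supported:
- **NIP is equally affected.** The protocol's own time course shows few early events.
- **Quality-of-life change would be measured from an on-treatment score.** Section 9.7 already says: "For all analyses, baseline value will be defined as the latest assessment prior to first study drug administration". A first questionnaire after first dose is therefore not a baseline, and handling of missing data is left to the analysis plan.
- **Patients who stop treatment in the first weeks are never enrolled.** The protocol gives no figure for this, and a new adverse event definition would not cure it.

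**What to change.** - Use one start point, first dose, in both Section 9.3.4.6 and Section 11, for recording and analysing stomatitis, NIP and other adverse events.
- For patients consented after first dose, abstract the interval from first dose to consent from the notes once consent is given. Enter events on the adverse event page with onset date, grade and course, not in medical history alone.
- Record the dates of first dose and of consent. Report how many patients consented after first dose, with a sensitivity analysis in those consented on or before it.
- Word the 24-hour expedited reporting of serious events that precede consent separately. Section 10 bars data collection before consent, so that clock cannot simply be moved to first dose.

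The cost is protocol wording, one flag on the case report form, a short chart abstraction for late-consented patients and one extra analysis. The drawback is that low-grade events abstracted in retrospect may be less complete than those recorded as they occur; the sensitivity analysis would help to show whether that matters.
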